10.1.2 Analysis of secondary endpoints

A summary of adverse events will be tabulated at baseline and during treatment. Analgesic use will be tabulated, converted into equivalent units, and changes in opiate equivalents before and after treatment will be compared. Descriptive statistics will be used to report the proportion of patients with changes in fatigue scores compared to baseline according to the worst fatigue item (Item #3) of the Brief Fatigue Inventory, at weeks 8 and 12. Descriptive statistics will also be used to report the proportion of patients with changes in pain interference scores compared to baseline based on the interference with activities item of the BPI, at weeks 8 and 12.

The time to radiographic progression and pain progression will be summarized using the cumulative incidence function. The percent change in PSA and bone turnover markers from baseline to 12 weeks will be summarized with descriptive statistics. Longitudinal assessments of BPI, and tiredness will be recorded and summarized over time.

Radiographic progression using PCWG2 criteria for bone scans, and RECIST for soft tissue/measurable disease will be used. The use of FDG PET imaging to demonstrate post-treatment effects is exploratory in nature – the impact of radium on the actual cancer cell is not known. Furthermore, there is no standard method for assessing post-treatment FDG PET changes that have been prospectively validated in prostate cancer. Because Ra-223 is a bone directed agent, bone lesions will be treated separately from soft tissue lesions. We will therefore examine multiple methods of examining post-treatment changes in FDG PET in order to explore which of those will most closely correlate with both pain response. These will include:

- A. We will analyze up to 5 bone lesions. Analysis will be performed either on HERMES or AWS workstation. For each lesion, a five point confidence scale will be employed as follows: 1: negative for tumor; 2: probably negative for tumor; 3: equivocal for tumor; 4: probably positive for tumor; 5: definitely positive for tumor. The SUV for each lesion will also be recorded along with its location.

Radium-223

MSKCC

PCCTC LOI: c13-124

IRB#: 14-098 A (5)

SUVpeak lean body mass will be determined in each of these lesions. The sum of these values at baseline will be compared to that of the sum at followup.

- B. If feasible, we will apply the above technique not only to 5 index lesions, but to all of the lesions, using the PET VCAR software or its equivalent.
- C. As a comparison, we will explore FDG PET interpretation using the PERCIST 1.0 criteria (*Wahl et al J Nucl Med 2009 50: 122S-150S*).

PSA decline will be reported per PCWG2 criteria ¹

10.2 Analysis Populations

10.2.1 *Evaluable population*

Responders will be defined by a 30% decline in the BPI worst pain item from baseline to week 8, with a confirmed reduction at week 12 without an escalation of the subject's pain regimen from Step 1 to Step 2 or Step 2 to Step 3 of the WHO analgesic ladder.

Patients with progressive pain will be defined by time until a ≥ 2 point increase in the average "worst pain" item on the BPI over a 7 day period compared to baseline is seen and confirmed at least 2 weeks later.

Patients who are neither categorized as pain responders or are categorized as ones with progressive pain will be recorded as non-responders.

All patients who meet eligibility criteria and receive at least 1 dose of study medication will be included in the main analysis of the response rate, even if there are major protocol deviations (e.g., incorrect treatment schedule or drug administration). Each patient will be assigned to one of the above categories.

10.2.2 *Safety population*

All patients enrolled in the study will be included in the safety analysis population and considered evaluable for toxicity and safety from the time of their first dose. Demographic and baseline characteristics for the safety population will be summarized by number and percent for categorical data (e.g., sex, race/ethnicity) and by descriptive statistics for continuous data (e.g., weight, vital signs, EKG readings, disease status).

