- Radiographic response will also be determined using FDG PET/CT to assess for treatment effect in bone. Section 10.1.2 discusses how response will be assessed.
- Time to pain progression, defined as time until a ≥ 2 point increase in pain compared to baseline confirmed at least 2 weeks later.
- Change in analgesic use assessed by the WHO analgesic ladder
- Changes in measure of tiredness measured by the worst fatigue item (item #3) from the Brief Fatigue Inventory. (see Appendix E)
- Changes in measures of pain interference as assessed on Brief Pain Inventory. (see Appendix F)
- Evaluate the short and long term toxicity to treatment

Statistical method

Primary Analysis

The primary objective of this phase II study is to determine the effect of Radium-223 on pain improvement for patients with symptomatic metastatic castration-resistant disease. The primary endpoint of the study is a 30% decline in the BPI worst pain item from baseline to week 8, with a confirmed reduction at week 12, without an escalation of the subject's pain regimen from Step 1 to Step 2 or Step 2 to Step 3 of the WHO analgesic ladder. We define this event as a response and propose declaring the treatment effective if the probability of a response in the population exceeds 0.20.

A maximum of 63 patients will be entered onto the study. A two-stage design that differentiates between response rates of 0.20 and 0.35 will be used to assess treatment efficacy. In the first stage of the study 27 patients will be enrolled. If at most 5 patients respond, accrual will be terminated. If at least 6 patients respond, an additional 36 patients will be entered onto the study. At the conclusion of this second stage, if at least 17/63 patients respond, the treatment will be declared effective. The probability of declaring the treatment effective is 0.10 when the response rate in the population is 0.20 and increases to 0.90 when the response rate is 0.35.

Secondary Analysis

Descriptive statistics will be used to report the proportion of patients with various changes in fatigue scores compared to baseline according to the worst fatigue item (Item #3) of the Brief Fatigue Inventory, at weeks 8 and 12. Descriptive statistics will also be used to report the proportion of patients with changes in pain interference scores compared to baseline based on the interference with activities item of the BPI, at weeks 8 and 12.

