Patients (n=100) with progressive CRPC with testosterone levels <50 ng/dL after orchiectomy or on androgen ablation therapy who have bone pain ≥ 2 on the BPI were assigned to 1 of 4 single-dose groups of 5 kBq/kg (corresponding to 6kBq/kg after implementation of the NIST) (n=26), 25 kBq/kg (corresponding to 28kBq/kg after implementation of the NIST) (n=25), 50 kBq/kg (corresponding to 55kBq/kg after implementation of the NIST) (n=25), or 100 kBq/kg (corresponding to 110kBq/kg after implementation of the NIST) (n=24) of Radium 223 administered IV.⁷ Follow-up visits were conducted at 2, 4, 8, 12, and 16 weeks post-injection to access the palliative response. At Week 8, patients with no palliative response could be withdrawn from the study. Additionally, patients were evaluated annually for up to 2 years after dosing for long-term safety and survival.

A statistically significant dose response occurred at Week 2 ($P=0.035$ [Jonckheere-Terpstra test]).⁶ At Week 8 there were 40%, 63%, 56%, and 71% pain responders (pain index ≤ 4) in the 5, 25, 50, and 100 kBq/kg groups (corresponding to 6,28,55 and 110kBq groups after implementation of the NIST) , respectively. Of the responders, 6/20 (30%), 8/19 (42%), 8/18 (44%), and 11/21 (52%) reached complete (pain index 1) or marked pain response (pain index 2), respectively.

At Week 8, the mean daily diary pain decreased by 30 mm average in the responder group, remained unchanged in the stable group, and decreased 12 mm in the pain progression group.⁷ The pain progression group was allowed to increase analgesics. Up to week 8, fewer patients in the higher dose groups (50 and 100 kBq/kg) (corresponding to 55 and 110 kBQ/Kg after implementation of the NIST) required in increases in analgesia compared to lower dose groups.

Mean pain relief duration of 44 days for higher-dose (50 and 100 kBq/kg) corresponding to 55 and 110 kBQ/kg after implementation of the NIST) groups, 28 days for 5 kBq/kg (corresponding to 6kBq/kg after implementation of the NIST, and 35 days for 25 kBq/kg (corresponding to 28kBq/kg after implementation of the NIST) dose groups.⁷ There was not a significant dose-response for pain relief duration.

BPI data showed significant dose-dependent treatment effect at the 8-week point ($P=0.040$ [Jonckheere-Terpstra test]).⁷ For patients with a pain response, there was a significant decrease in BPI pain severity for all 4 dose groups ($P=0.05$, $P=0.001$, $P=0.002$, and $P=0.0006$ [Wilcoxon signed rank test]).

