2.2 Secondary Objectives

2.2.1 To assess the impact of treatment on markers of bone turnover

Radium-223

MSKCC

PCCTC LOI: c13-124

IRB#: 14-098 A (5)

- 2.2.2 To assess the impact of treatment on PSA
- 2.2.3 To assess the impact of treatment on time to radiographic progression
- 2.2.4 To assess the impact of treatment on quantifiable imaging biomarkers assessing bone metabolism
- 2.2.5 To assess the impact of treatment on tiredness
- 2.2.6 To assess the toxicity of treatment
- 2.2.7 To assess the impact of treatment on pain interference specifically evaluating its affect on general activity and sleep as measured by the BPI
- 2.2.8 To assess the impact of treatment on time to pain progression
- 2.2.9 To assess the impact of treatment on change in analgesic use

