During the Run-In Period, subjects will self-report pain and fatigue using a PRO instrument daily for 7 days and record analgesic medication information on a paper pain medication diary to establish that their BPI average baseline pain score is ≥ 3 as measured for a minimum of 4 of the 7 days (See Appendix I for instructions). This data will be used to confirm eligibility based on pain experience. Upon confirmation of eligibility, the subject's registration will be completed and the subject must start treatment within 5 days of registration.

Radium-223

MSKCC

PCCTC LOI: c13-124

IRB#: 14-098 A (5)

If run-in requirements are not met with respect to pain score, subjects may be eligible to rescreen at a later time.

5.2 Treatment/Intervention Period (Week 1, Day 1 to Week 25, Day 169 (treatment visits have a window of ± 3 days))

Unless otherwise specified, all visit procedures are to be performed prior to Radium-223 administration on the day of the visit. Radium -223 will be administered every 4 weeks for 6 doses at a dose of (50 kBq (0.00135 mCi) (55kBq (.0015 after NIST update) Because ALSYMPACA did not assess radiographic assessments during treatment, neither radiographic progression nor PSA progression should be used to discontinue treatment. However, patients are *permitted, per FDA labeling*, to be maintained on other anti-cancer therapies in addition to Radium-223 provided that these are not changed in the midst of pain assessments. Other-cancer therapies must be initiated 4 weeks prior to the run-in period. Patients with an increase in pain of 2 points on their BPI worst pain item compared to baseline and confirmed at least 2 weeks later will be considered to be treatment failures and will be taken off trial. In the absence of clinical progression, patients will continue to receive all six treatments, and will continue treatment until clinical progression, unacceptable toxicity, or any criteria in Section 5.6 Removing Patients from the Protocol. Patients will return to the clinic every 4 weeks for the following assessments:

- Physical exam
- ECOG performance status
- Vital signs [body temperature, blood pressure, pulse, respiratory rate, weight]
- ECG (as clinically indicated – not required at every visit)
- Lab tests [hematology, serum biochemistry, PSA, bone markers (to be done at the Wk 9 and Wk 13 visit)]
- Clinician reported adverse events and concomitant medications will be monitored continuously throughout the study

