8.2 Secondary endpoints

- Bone-ALP response will be described as:
 - Percentage of change from baseline to 12 weeks (or earlier for those who discontinue study therapy)
 - Maximum change (rise or fall) in bone-ALP during the treatment period reported for each patient as a waterfall plot
- Changes in total-ALP will be defined as for bone-ALP above
- PSA decline will be reported on all patients. Using PCWG2 guidelines ¹, the percentage of change in PSA from baseline to 12 weeks, as well as the maximum decline in PSA will be reported for each patient using a waterfall plot.
- Progression, for those patients showing an initial decline in PSA from baseline, is defined as an increase in PSA that is $\geq 25\%$ and ≥ 2 ng/mL above the nadir, and which is confirmed by a second value 3 or more weeks later (i.e., a confirmed rising trend).
- Progression, for those patients with no decline in PSA from baseline, is defined as an increase in PSA that is $\geq 25\%$ and ≥ 2 ng/mL after 12 weeks. Note: PSA progression as such will not lead to study discontinuation
- Time to First Radiographic or Clinical Progression (TTFROCP) based on RECIST version 1.1 and Prostate Cancer Working Group 2 (PCWG2) definitions
- Changes in other bone markers:
 - Serum C-telopeptide (sCTX-1)
 - N-terminal propeptide of procollagen type 1 (PINP)
- Radiographic response through the RECIST criteria 1.1 will also be determined using FDG PET/CT to assess for treatment effect in bone.
- Time to pain progression, defined as time until a ≥ 2 point increase in pain compared to baseline confirmed at least 4 weeks later.
- Change in analgesic use assessed by the WHO analgesic ladder
- Changes in measure of tiredness measured by the worst fatigue item (item #3) from the Brief Fatigue Inventory.
- Measures of pain interference specifically evaluating its affect on general activity and sleep as assessed on BPI
- Evaluate the short and long term toxicity to treatment

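### Time to pain progression counts only a rise in the pain score, so analgesic escalation that holds the score down hides events and lowers the reported incidence

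*Combined protocol and SAP*

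**What the plan says.** Secondary objective 2.2.8 is "To assess the impact of treatment on time to pain progression". Three places define the endpoint:

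- Synopsis, secondary criteria for evaluation: "Time to pain progression, defined as time until a ≥ 2 point increase in pain compared to baseline confirmed at least 2 weeks later".
- Section 8.2: the same 2-point rise, but "increase in pain compared to baseline confirmed at least 4 weeks later".
- Section 10.2.1: "Patients with progressive pain will be defined by time until a ≥ 2 point increase in the average 'worst pain' item on the BPI", taken over a 7-day period and confirmed at least 2 weeks later.

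The rule in section 5.2 for taking a patient off trial is also based on the score: "Patients with an increase in pain of 2 points on their BPI worst pain item compared to baseline", confirmed at least 2 weeks later.

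Section 10.1.2 says that time to pain progression will be summarised with the cumulative incidence function. It names no competing event and gives no rule for analgesic escalation.

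By contrast, the response definition in 8.1, 10.1.1 and 10.2.1 fails if the regimen moves from Step 1 to Step 2 or from Step 2 to Step 3 of the WHO ladder. Section 5.7 lists modification of the pain regimen under permitted treatment, and nothing bars escalation after enrolment. Analgesic use is a separate objective (2.2.9), reported by WHO step (8.2) and by opiate equivalents (10.1.2).

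**The concern.** Worsening bone pain can be met with more analgesia. If that works, the score stays flat and a score-only endpoint records nothing. The plan guards the favourable outcome (response) against this masking but leaves the unfavourable one (progression) open to it, within the same section 10.2.1.

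What is at stake is the answer to objective 2.2.8. The estimate describes radium-223 together with whatever analgesic escalation took place. A reader will tend to take it as a statement about how soon pain worsens. With a single arm, no comparator would show the difference.

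**Working it through.** **1. The rules side by side**

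| Place | Score criterion | Confirmation | Analgesic condition |
|---|---|---|---|
| Synopsis, pain progression | rise of at least 2 points | at least 2 weeks later | none |
| 8.2, pain progression | rise of at least 2 points | at least 4 weeks later | none |
| 10.2.1, pain progression | rise of at least 2 points, 7-day average worst pain | at least 2 weeks later | none |
| 5.2, off-trial rule | rise of 2 points, worst pain | at least 2 weeks later | none |
| 8.1, 10.1.1, 10.2.1, response | 30% fall at week 8 | reduction confirmed at week 12 | no WHO-step escalation |

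**2. One patient traced through the plan.** A man enters on Step 1. His pain worsens, he is moved to Step 3, and his average worst pain stays less than 2 points above baseline. He is not a responder, because the step rose. He is not a pain progressor either, because the score did not. Section 10.2.1 then records him as a non-responder, and he adds nothing to the pain-progression curve while his score stays below that threshold. His escalation appears only in the separate analgesic summaries.

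**3. Direction and possible size.** Effective escalation can remove or delay a score event but cannot create one. If a share m of the patients with true worsening is masked, then

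reported incidence = true incidence × (1 − m).

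The documents give neither the true incidence nor m, so every entry below rests on assumed inputs:

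| True incidence (assumed) | m = 10% | m = 25% | m = 50% |
|---|---|---|---|
| 20% | 18% | 15% | 10% |
| 30% | 27% | 22.5% | 15% |
| 40% | 36% | 30% | 20% |
| 50% | 45% | 37.5% | 25% |

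In patients, at 40% and m = 25%: 63 × 0.40 = 25.2 true events and 25.2 × 0.75 = 18.9 reported, so about 6 are hidden.

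**4. The primary decision.** The plan states no design figure for pain progression. Its only design figures belong to the primary endpoint: continue if at least 6 of 27 respond, and declare the treatment effective if at least 17 of 63 respond. Summing P(X1 = x) × P(X2 ≥ 17 − x) over x = 6 to 27, with X1 ~ Bin(27, p) and X2 ~ Bin(36, p), gives 0.0999 at p = 0.20 and 0.902 at p = 0.35. These match the stated 0.10 and 0.90. Whether a patient without a response is filed as progressive pain or as a non-responder does not change the number of responders, so the decision is untouched.

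**The case against.** Time to a score rise, whatever analgesia is given, is a legitimate treatment-policy quantity, and it matches the rule in 5.2. Escalation is not ignored, because it has its own objective and two planned summaries. Worsening can also be recorded as symptomatic or clinical progression (5.5, 5.6) and in time to first radiographic or clinical progression (8.2). The endpoint is unpowered and descriptive.

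Most of this stands, and it limits the point. It does not remove it: group-level analgesic summaries do not correct a time-to-event curve, and the plan neither says that the endpoint is meant to disregard analgesia nor explains why response is handled differently.

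A reader might go further in three ways that the documents do not support.

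- **That a masked patient never progresses.** This holds for this endpoint only, and only while the score stays below a 2-point rise. Pain that later breaks through and is confirmed still counts.
- **That the background study demonstrates the masking.** Section 1.2.1 reports that mean diary pain "decreased 12 mm in the pain progression group" and that "The pain progression group was allowed to increase analgesics". But this is a group mean on a visual analogue diary, not the BPI worst-pain item, and section 1.2.1 itself calls that study's pain measures non-standard. The stable group was unchanged, so a fall in the progression group may be a misprint. On an assumed 0–100 mm scale, 12 mm is 1.2 points. As printed, the group sits 2 + 1.2 = 3.2 points below the threshold; had the word been the opposite, 2 − 1.2 = 0.8 points below it, and a rise is no evidence of masking. The point does not depend on this figure.
- **That the bias has a known size.** No escalation or progression rate is given.

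**Conclusion.** The point holds as a matter of definition and direction. All three definitions count only a score rise, escalation is permitted, and the cumulative incidence of pain progression is therefore biased downward as a measure of pain worsening. This assumes only that some escalations on study succeed in holding the score down. The amount cannot be computed from the documents; the table above is an illustration.

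The consequence is confined to a secondary, descriptive endpoint. It would be wrong to infer that the primary result or the 17/63 decision is affected, because the primary endpoint already excludes step escalation.

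Separately, the same endpoint has a definite contradiction in its confirmation interval (at least 2 weeks in the synopsis and 10.2.1, at least 4 weeks in 8.2), which must be reconciled.

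**What to change.** For the analysis endpoint only, in the synopsis, 8.2 and 10.2.1:

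- Add a composite time to pain progression, reported together with the score-only version. It is the first of (a) the confirmed score rise or (b) a sustained increase over baseline in WHO analgesic step, taken from the analgesic diary.
- Confirm (b) over the same fixed minimum interval as (a). Confirmation at the next assessment would not be stable: the schedule has adjacent weeks such as 8 and 9, while the schema mentions 12-week spacing later on.
- Do not count drug changes recorded as made for side effects, since 5.7 foresees opioid rotation.
- Because a patient on Step 3 at baseline cannot rise a step, add a sensitivity analysis that uses a pre-specified increase in the opiate equivalents already planned in 10.1.2.
- Reconcile the 2-week and 4-week confirmation intervals.

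The off-trial rule in 5.2 is not touched.

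The cost is wording and one or two derived variables. The step is graded at enrolment, and the diary is kept daily in the pain-assessment periods. The text does not say whether the reason for an analgesic change is captured; if it is not, one data field is needed. The reported time to progression on the composite will be shorter, and some step changes not caused by pain may still count as events.

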10.3 Safety Analysis

10.3.1 *Evaluation of adverse events*

Pain will be assessed using PBI and fatigue by the BFI.

Treatment-emergent adverse events will be translated from investigator terms to NCI CTCAE v4.0 terminology and summarized (number and percentage of patients) for all patients who receive at least 1 dose. Adverse event summaries will be organized by body system, frequency of occurrence, intensity (i.e., severity grade), and causality or attribution. Patients who experience an adverse event more than once will be counted only once. The occurrence with the maximum severity will be used to calculate intensity.

10.3.2 *Evaluation of serious adverse events and premature withdrawals*

Adverse events deemed serious and those resulting in treatment withdrawal or death will be summarized separately.

10.3.3 *Evaluation of laboratory parameters and assays*

Selected clinical laboratory parameters will be summarized and clinically significant changes from baseline will be discussed.

10.3.4 *Extent of exposure*

Treatment exposure will be summarized for all patients, including dose administration, number of cycles, or delays, and duration of therapy.

